#### **4.2 Research Design**[L][SEP]

The study will be a double-blind, repeated measures design. In order to minimize group differences, participants will be matched according to age and weight and be randomized on a 1:1:1:1 basis to one of four groups: Creatine + Caffeine (CR-CAF; 0.1 g/kg of creatine monohydrate powder + 3 mg/kg of caffeine [micronized powder]); Creatine (CR; 0.1 g/kg of creatine monohydrate powder + 3 mg/kg of caffeine placebo [micronized cellulose powder]), Caffeine (CAF; 3 mg/kg of caffeine + 0.1 g/kg of creatine monohydrate placebo [maltodextrin]) or placebo (PLA; 0.1g/kg creatine monohydrate placebo + 3 mg/kg of caffeine placebo). An individual, blinded to supplement and group allocation, will be responsible for the preparation of study kits. Each study kit will contain the participants supplement for the duration of the study, detailed supplementation instructions, measuring spoons, supplementation compliance log, daily caffeine consumption log and a resistance training log. Supplement powders will be similar in energy content, color, taste, texture, and appearance. The creatine dosage of 0.1 g/kg has previously been shown to be effective for increasing muscle mass and muscle performance. The caffeine dosage of 3 mg/kg has been shown to increase muscle performance. Participants will be instructed to refrain from additional caffeine sources  $\geq 3$  hour prior to consuming their supplement so that a valid estimate regarding the effects of caffeine supplementation on muscle can be made. On training days, participants will mix their supplement powder in water and consume the solution 60 minutes prior to exercise. Sixty minutes was chosen because this is the approximate time it takes for peak plasma caffeine concentrations to occur after caffeine ingestion and pre-exercise

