creatine supplementation has a beneficial effect on muscle performance. On non-training days, participants will refrain from consuming their supplement as the purpose of the study is to investigate the effects of pre-exercise creatine and caffeine co-supplementation. Adherence with the supplementation protocol will be assessed using compliance logs. Habitual daily caffeine consumption will be recorded using caffeine logs. Upon completion of the study, participants will be asked whether they thought they were administered creatine and caffeine, creatine, placebo, or unsure about what supplement they consumed. The primary dependent variables that will be measured at baseline and after the intervention include: (1) muscle thickness (elbow and knee flexors and extensors; ultrasonography), (2) muscle strength (1-RM leg press, chest press) and (3) muscle endurance (leg press and chest press; maximum number of repetitions performed for 1 set using 50% baseline 1-RM). In addition, participants will fill out a 3-day food diary during the first and final week of supplementation and training to determine whether total energy (kcal) and macronutrient intake changed over time.

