#### **4.3 Resistance Training Program**

Participants will follow the same periodized, resistance training program for 6 weeks. The program will consist of three sets of 6, 8, 10 repetitions to muscle fatigue in order. Resistance training will start on the first day of supplementation and will consist of a split routine involving whole body musculature. Day 1 will involve chest and biceps musculature and include the following exercises in order: machine-based chest press, free weight incline bench press or dumbbell press, free-weight flat dumbbell press, machine-based pec-dec, free-weight standing barbell curl, free-weight alternate arm dumbbell curl and machine-based preacher curl. Day 2 will involve leg and core musculature and include the following exercises in order: free-weight squat, machine-based leg press, machine-based leg extension, machine-based leg curl, machine-based calf raise, and

machine-based weighted abdominal crunches. Day 3 will serve as a rest day from training. Day 4 will involve back and triceps musculature and include the following exercises in order: body weight or weight-assisted chin-ups, machine-based seated row, machine-based lat pull-down, free-weight alternate dumb-bell row, free-weight close-grip bench press, machine-based cable triceps bar extension, and machine-based cable triceps rope extension. Day 5 will involve shoulder and core musculature and include the following exercises in order: free-weight dumbbell press, free-weight upright row, free-weight shrugs, free-weight or machine based lateral deltoid flys, free-weight or machine-based rear deltoid flys and machine-based weighted abdominal crunches. Day 6 will serve as a rest day from training. This cycle will be repeated for 6 weeks. Participants will maintain training logs to ensure adherence and compliance to the study and to determine total training volume (load x repetitions x sets).

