#### 4.5 Statistical Analysis

A 4 (group: CR-CAF vs. CR vs. CAF vs. PLA) x 2 (time: pre- vs. post- training) repeated measures analysis of variance (ANOVA) will be used to determine differences between groups over time for the dependent variables of muscle thickness, muscle strength, muscle endurance and diet. If significant interactions are detected, a one-factor ANOVA on absolute change scores ( $\Delta = \text{post mean} - \text{pre mean}$ ) will be performed to confirm the interaction. A one-factor ANOVA will be used to assess baseline data and training volume. Significance is set *a priori* at an alpha level of  $p < 0.05$ . Cohen's *d* effect size (ES) for significant main effects and interactions will be calculated as  $\text{post-training mean} - \text{pre-training mean} / \text{pooled pre-training standard deviation mean}$  (Cohen, 1992). An ES of 0.00-0.19 is considered trivial, 0.20-0.49 is considered small, 0.50-0.79 is considered moderate, and  $\geq 0.80$  is considered large (Cohen, 1992). Statistical analyses will be performed using IBM® SPSS® Statistics, v. 24.

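### The Cohen's d set for a significant group x time interaction is a pre-to-post change with no between-arm term, so in an active arm it adds the training gain to the supplement effect

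*Protocol*

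**What the plan says.** Section 4.5 of the protocol plans a 4 (group) x 2 (time) repeated-measures ANOVA, which "will be used to determine differences between groups over time for the dependent variables of muscle thickness, muscle strength, muscle endurance and diet". A significant interaction has a set follow-up: "If significant interactions are detected, a one-factor ANOVA on absolute change scores".

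The same paragraph then fixes the effect size. Cohen's d "effect size (ES) for significant main effects and interactions will be calculated as" post-training mean minus pre-training mean, divided by a pooled pre-training SD. One scale is attached to it: "An ES of 0.00-0.19 is considered trivial, 0.20-0.49 is considered small, 0.50-0.79 is considered moderate", and 0.80 or more is large. No other measure of magnitude is defined, and the text does not say whether d is computed per arm or over all arms.

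Two other sections matter here. Section 4.2 says that "the purpose of the study is to investigate the effects of pre-exercise creatine and caffeine co-supplementation", with participants "randomized on a 1:1:1:1 basis to one of four groups", one of them placebo. Section 4.3 adds: "Participants will follow the same periodized, resistance training program for 6 weeks". The placebo arm therefore trains too.

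**The concern.** A group x time interaction is a difference between arms in their change over time. The formula stops at the change and never compares arms. It suits the time main effect. It does not measure the interaction, nor a group main effect.

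Because every arm trains, an active arm's pre-to-post d contains the gain that training alone would have produced. If that figure is reported and graded as the size of the interaction, training is credited to the supplement. A small benefit can be published as moderate or large, and this d is the only magnitude that section 4.5 defines for a positive result.

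**Working it through.** **Which test the trial was sized on.** Inputs from section 4.1: f = 0.25, alpha 0.05, 0.8 (written as a beta value, read here as power) and N = 48. From section 4.5: k = 4 groups, m = 2 times. The protocol gives no pre-post correlation; I assume 0.5. For the interaction, the noncentrality is f² x N x m / (1 - r) = 0.0625 x 48 x 2 / 0.5 = 12, with 3 and 44 df. Power is 0.803 at N = 48 and 0.760 at N = 44. So 48 reproduces as the sample size for the group x time interaction, the effect whose magnitude the formula fails to measure.

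**What the formula estimates.** Let g be the placebo arm's gain and s the extra change in an active arm, both in pre-training SD units.

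- Placebo arm: d = g
- Active arm: d = g + s
- Supplement effect: s

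The active arm's d exceeds the supplement effect by exactly the placebo arm's d. With s = 0, an active arm has the same expected d as placebo: small at g = 0.2, moderate at 0.5, large at 0.8.

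**Average size.** Assume 12 per arm, bivariate normal data and the SD pooled over four arms (44 df). The mean change is then independent of the pooled pre-training SD, so E[d] = (g + s) x c, with c = E[1/s_pooled] = 1.0175 for a true SD of 1. The correlation drops out.

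| True benefit s | d in CR at g = 0.2 / 0.5 / 0.8 | Between-arm d |
|---|---|---|
| 0.30 (small) | 0.51 / 0.81 / 1.12 | 0.31 |
| 0.50 (moderate) | 0.71 / 1.02 / 1.32 | 0.51 |
| 1.00 (large) | 1.22 / 1.53 / 1.83 | 1.02 |

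For example, (0.5 + 0.3) x 1.0175 = 0.814. Pooling over two arms only (22 df, c = 1.0358) changes little: for s = 0.30, 0.52 / 0.83 / 1.14 against 0.31.

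The last row is the planning effect if both creatine arms share the benefit. The interaction deviations of the cell means are then ± s/4, so f = 0.25 means s = 1.0. There the figure is 20, 50 or 80% too high, but the average grade is large either way.

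**In trials where this d would be reported.** The effect size is computed only after a significant result. I simulated trials with both creatine arms shifted by 0.30 SD and kept those with a significant interaction (F on change scores, 3 and 44 df). Such trials make up 11.5%, 23% and 44% of all trials at r = 0.5, 0.8 and 0.9. Each cell below gives the values at g = 0.2 / 0.5 / 0.8; simulation error is about 0.01 at r = 0.5 and less at higher r.

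| r | Mean d in CR | Mean between-arm d | Excess |
|---|---|---|---|
| 0.5 | 0.69 / 1.00 / 1.32 | 0.66 / 0.65 / 0.67 | 0.03 / 0.35 / 0.65 |
| 0.8 | 0.61 / 0.92 / 1.23 | 0.51 / 0.50 / 0.51 | 0.10 / 0.41 / 0.72 |
| 0.9 | 0.56 / 0.87 / 1.17 | 0.41 / 0.41 / 0.41 | 0.15 / 0.46 / 0.76 |

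The share of these trials in which CR's d falls in a higher band than the between-arm d of the same trial is about 25/45/53% at r = 0.5, 38/81/86% at 0.8 and 49/96/98% at 0.9.

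**The case against.** The strongest reply is that the effect size is descriptive and the between-group question is already handled: section 4.5 tests the interaction and then compares change scores across arms. If d is computed per arm with a common SD, placebo gets one too, and a reader can subtract. That is true, and it is why inference is untouched. But the protocol attaches the formula and the grading scale to the interaction itself, plans no subtraction, and does not say which arms are pooled.

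Second, the text does not say that d is computed per arm. If it is taken over all arms, the CR figures above do not apply. The defect remains, because d is then the average training gain plus the average supplement effect and still contrasts nothing.

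Third, some of the inflation comes from reporting only after significance. At a true 0.30 SD, the between-arm d in significant trials averages about 0.66 at r = 0.5 and 0.51 at r = 0.8, both moderate. This stands: the corrected formula alone does not remove selection. The excess column is the part due to the formula, since both measures come from the same selected trials.

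Fourth, a material error needs a training gain of about 0.5 SD or more, and a changed average grade needs a benefit well below the planning effect. The protocol gives no gain, and section 4.1 recruits trained men to limit neuromuscular learning, which may keep gains modest. This also stands as a limit on size. It does not make the definition right.

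**Conclusion.** The point holds. As written, section 4.5 assigns to a significant interaction a quantity that does not measure it, on either reading of how d is computed. At an assumed true benefit of 0.30 SD, and in trials with a significant interaction, an active arm's d exceeds the between-arm d by 0.03 to 0.15 for a 0.2 SD training gain, by 0.35 to 0.46 for 0.5 SD and by 0.65 to 0.76 for 0.8 SD. The error is therefore small for a modest gain and material from about 0.5 SD upward.

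These sizes rest on assumed gains and correlations, normal data, 12 completers per arm and both creatine arms benefiting equally. That the formula lacks a between-arm term needs none of these assumptions. This is a reporting definition that should be corrected. It does not threaten the tests, alpha or the sample size.

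**What to change.** In section 4.5, split the effect-size definition in two.

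- **Interaction:** d is the difference between two named arms in mean change (post minus pre), divided by the pooled pre-training SD, stating which arms are pooled. The grading scale applies to this figure. It completes the contrast that the change-score ANOVA already tests.
- **Time main effect:** keep the pre-to-post d, labelled as within-group response (training plus any supplement effect). State that it is not used for a group main effect.

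It would also help to report the between-arm d with a 95% CI for the primary variables whether or not the interaction is significant, because that removes the selection noted above. This is an improvement beyond the correction itself.

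The cost is two sentences, with no new data and no change to the tests or to N.

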## 4. Methods

### 4.1 Participants

An *a priori* power analysis (G\*Power v. 3.1.5.1) indicated that 48 participants are required. This calculation is based on a small effect size (Cohen's  $f = 0.25$ ), an alpha level of .05, and a  $\beta$ -value of 0.8 for a repeated measures, within-between analysis of variance (ANOVA) design. Males (18-30 years of age) who have been performing structured resistance training ( $> 3x/week$  for  $\geq 6$  months) prior to the start of the study will be recruited. Resistance trained participants are being recruited to help reduce the influence that neuromuscular learning has on changes in muscle mass and muscle performance over time. Prior to the start of supplementation and training, participants will fill out a questionnaire which assesses their readiness for participation in resistance training. Participants will also fill out a leisure time exercise questionnaire, which indicates the average number of times that strenuous (i.e. heart beats rapidly), moderate (i.e. not exhausting), and mild exercise (i.e. minimal effort) is performed per week. Participants will be excluded from the study if they have taken medications that affect muscle biology or creatine monohydrate  $\leq 12$  weeks prior to the start of resistance training and supplementation; if they have diseases that are known to affect muscle biology (i.e. Crohn's Disease), if they have pre-existing kidney or liver abnormalities, or if they plan to travel  $\geq 1$  week during the study where they have no access to a fitness facility. Habitual caffeine consumers are being included because regular caffeine consumption does not negate the beneficial effects of caffeine supplementation. Furthermore, habitual caffeine consumers who withdraw from caffeine may experience adverse symptoms which could negatively affect exercise performance. Participants will be instructed not to change their habitual diet or engage in additional physical activity that is not part of their normal daily routine or consume non-steroidal anti-inflammatory drugs during resistance training and

supplementation, as these interventions can affect muscle protein synthesis. The study will be approved by the Research Ethics Board at the University of Regina. Participants will be informed of the risks and purposes of the study before written consent is obtained.

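### Section 4.5 calculates effect sizes only for results with p < 0.05, so supplement effect sizes run too large on average and a non-significant interaction gets none

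*Protocol*

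**What the plan says.** Protocol section 4.5 plans a 4 (group) by 2 (time) analysis for each dependent variable: "repeated measures analysis of variance (ANOVA) will be used to determine differences between groups over time". The supplement effect sits in the group-by-time interaction. Two later steps depend on significance.

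- The follow-up on change scores: "If significant interactions are detected, a one-factor ANOVA on absolute change scores".
- The effect size: "effect size (ES) for significant main effects and interactions will be calculated". It is defined as the pre-to-post change in the mean over a pooled pre-training SD, then graded trivial (below 0.20), small (0.20-0.49), moderate (0.50-0.79) or large (0.80 and above).

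The threshold is p < 0.05 ("Significance is set *a priori* at an alpha level of" that value in section 4.5, and "an alpha level of .05" in section 4.1). Nowhere does the protocol provide an effect size, group difference or confidence interval for a non-significant interaction. Section 4.2 lists three kinds of primary variable, which make eight measures: four muscle-thickness sites, two 1-RM tests and two endurance tests.

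**The concern.** The same data decide whether an effect size is reported and how large it is. Samples in which chance enlarged the group differences pass the test more often, so the effect sizes that survive are too large on average. A correct formula for d would not remove this, because the bias comes from the selection.

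The other side of the rule is a gap. With 12 men per arm a real but modest supplement effect will often miss p < 0.05. That variable then has no graded supplement effect, and a reader cannot tell a precise null from an imprecise estimate of something useful. The trivial-to-large grade is the protocol's only stated measure of how big an effect is, so the distortion and the gaps fall on the figure that readers will use.

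**Working it through.** **Inputs from the protocol.** N = 48, f = 0.25, alpha 0.05, and a power of 0.8 (printed as a beta, "value of 0.8 for a repeated measures, within-between analysis of variance (ANOVA) design") from section 4.1. Four arms at 1:1:1:1 from section 4.2, so 48/4 = 12 per arm. The p < 0.05 condition and the grades come from section 4.5.

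**Assumed, because the protocol does not give them.** Pre-post correlation rho, shown from 0.5 to 0.9. Pre-training SD set to 1. Both creatine arms better than both non-creatine arms by delta in change. A common training gain of 0.3 or 0.5 SD where the pre-to-post d is examined.

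**1. The plan's own figure.** For the interaction with k = 4 groups and m = 2 times, lambda = f² N m/(1 - rho), df = (k-1)(m-1) = 3 and (N-k)(m-1) = 44. With rho = 0.5, lambda = 0.0625 × 48 × 2/0.5 = 12 and power is 0.803. At N = 44 power is 0.760. So 48 is the smallest multiple of 4 that reaches 0.80, and the figure reproduces.

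**2. What f = 0.25 means as a difference in change.** With arm deviations of +delta/2 and -delta/2 in change, f² = (delta/2)²/4, so delta = 4f = 1.0 pre-training SD. Check: the change score has variance 2(1 - rho) = 1 at rho = 0.5, and lambda = 12 × 4 × 0.5²/1 = 12, as in step 1. Section 4.1 calls this effect small. On the section 4.5 scale a difference of 1.0 SD would be large.

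**3. Power for smaller true differences.** lambda = 12 × 4 × (delta/2)²/[2(1 - rho)], that is 1.08/[2(1 - rho)] for delta = 0.30 and 3/[2(1 - rho)] for delta = 0.50.

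**4. The filter applied to the between-group difference in change.** Simulated trials with 12 per arm, keeping those with interaction p < 0.05. Averaged over all trials the estimate is unbiased. Among significant trials:

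| True difference | rho | lambda | Power | Mean estimate if significant | Ratio to truth |
|---|---|---|---|---|---|
| 0.30 | 0.5 | 1.08 | 0.115 | 0.64 | 2.1 |
| 0.30 | 0.7 | 1.8 | 0.165 | 0.56 | 1.9 |
| 0.30 | 0.8 | 2.7 | 0.231 | 0.50 | 1.7 |
| 0.30 | 0.9 | 5.4 | 0.436 | 0.40 | 1.3 |
| 0.50 | 0.5 | 3.0 | 0.254 | 0.80 | 1.6 |
| 0.50 | 0.7 | 5.0 | 0.406 | 0.68 | 1.4 |
| 0.50 | 0.8 | 7.5 | 0.580 | 0.61 | 1.2 |
| 0.50 | 0.9 | 15 | 0.889 | 0.52 | 1.05 |
| 1.00 (f = 0.25) | 0.5 | 12 | 0.803 | 1.09 | 1.09 |

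For a true 1.0 SD the ratio falls to 1.02 at rho = 0.7 and 1.00 from rho = 0.8. At rho = 0.5 the ratio for other values of f is 1.43 at f = 0.15 (power 0.355) and 1.83 at f = 0.10 (power 0.17). It is almost the same for four different assumed patterns of arm effects.

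**5. The filter applied to the protocol's own d.** This is the pre-to-post d in the combined-supplement arm, true difference 0.30, given a significant interaction:

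| Training gain | rho 0.5 | rho 0.7 | rho 0.8 | rho 0.9 |
|---|---|---|---|---|
| 0.5 SD | 1.21 | 1.16 | 1.12 | 1.06 |
| 0.3 SD | 1.30 | 1.22 | 1.16 | 1.08 |

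A separate simulation gave 1.07 to 1.32 overall, so the second decimal is uncertain by about 0.02. The ratio is lower than in step 4 because the common training gain, which the interaction test does not select on, is part of this d.

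**6. How often a supplement effect size is missing.** One minus power: at rho = 0.5 about 88% of trials for a true 0.30 SD, about 75% for 0.50 SD and about 20% at the design effect.

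**The case against.** The best reply is that the trial is planned at 80% power, where inflation of the between-group contrast is only 9% at rho = 0.5 and negligible from rho = 0.8. The statistic that the protocol actually computes is inflated less again. Both points stand and limit the size of the finding. They do not remove it, because the design effect equals a 1.0 SD difference in change in this pattern. Effects that section 4.5 would itself call small or moderate lie well below it, where the filter acts hardest unless the pre-post correlation is high.

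A reader might infer more than the protocol supports:

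- **That every reported supplement effect is too large.** It holds on average only. At f = 0.25 and rho = 0.5, about 38-40% of significant contrasts still fall below the truth.
- **That non-significant variables get no effect size at all.** The rule also covers main effects, so a significant time effect still earns a d. With a 0.5 SD training gain and a true 0.30 SD difference, under 1% of simulated trials had no d of either kind. With a 0.3 SD gain it was about 12% at rho = 0.5 and about 2% or less from rho = 0.7. That d describes training, not the supplement.
- **That a true small effect is upgraded to moderate on the protocol's scale for correlations up to 0.8.** The scale is applied to a pre-to-post d, not to the between-group contrast. Even for the contrast, the mean at rho = 0.8 is about 0.495, on the boundary.
- **That the results could not be pooled.** Nothing says that group means and SDs will be withheld, and pooling can use those.

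**Conclusion.** The point holds in a limited form. The protocol itself fixes the rule, so this is not a detail left to an analysis plan that is not shown. Conditioning d on p < 0.05 makes supplement effect sizes too large on average and leaves a non-significant interaction without one.

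The bias is modest at the design effect. It becomes substantial for the between-group contrast when the true difference is 0.30 to 0.50 SD and the pre-post correlation is not high, and it is smaller for the pre-to-post d as defined. All these ratios rest on the assumed correlation, training gain and pattern of arm effects, none of which the protocol states. The hypothesis tests are unaffected. What suffers is the reported size of effect, so this is an improvement that should be made and not an error that invalidates the analysis.

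**What to change.** In section 4.5, remove the word significant from the effect-size rule and change the formula with it. Deleting the word alone would give a pre-to-post d for every variable, which still mixes training with supplement and is not a comparison of groups.

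Suggested content: for each primary variable, whatever its p-value, report the between-group difference in change divided by the pooled pre-training SD, with a 95% confidence interval, for contrasts named in advance. Show the trivial-to-large label only beside that interval.

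The interval matters at this sample size. For two arms of 12 at rho = 0.5, the standard error of the difference in change is √(1/12 + 1/12) = 0.41 SD. The half-width is about 2.02 × 0.41 = 0.82 SD (44 df, treating the SD in the denominator as known), which is wider than any of the bounded label bands.

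Cost: a reworded sentence and formula and a longer results table. No new data, participants or tests.
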